Short et al describes a quantifiable anatomical explanation for incomplete or failed anaesthesia from FNB or FICB in patients with #NOF. Several studies demonstrate that the FN block and FICB do not reliably block the obturator nerve or the lumbar plexus [16-22]. Distally, the high articular branches of the FN and AON are consistently located between the anterior inferior iliac spine and the iliopubic eminence [15]. The articular branches of the ON are located close to the inferomedial acetabulum. [15,23]. Subsequently the pericapsular nerve group block (PENGB) was designed to target the articular branches of the FN and AON by infiltrating the sub-psoas space at the level of the iliopubic eminence [23]. A case series of 5 consecutive patients with #NOF at Toronto Western Hospital was published in November 2018 and demonstrated the feasibility and efficacy of this block [23]. There is no published data describing the duration of analgesia provided by the PENG block.

The PENGB has subsequently been adopted by several practitioners at Lismore Base Hospital for the treatment of #NOF. We believe there is a study ongoing in peri-operative patients comparing PENGB to FICB in Toronto. We are not aware of any research into the utilisation of the PENGB in the emergency department setting. Searches of multiple study registries reveal no ongoing trials.

A retrospective study of patients that received regional anaesthesia for # NOF at LBH in the first 4 months of 2019 was performed. This data included 40 patients that received regional anaesthesia in ED, 6 of whom received a PENG block.

In this audit, patients' total opioid requirements from time of block to time of operation were recorded and converted to oral morphine equivalents using the ANZCA Faculty of Pain Opioid Calculator.

This audit found that patients receiving PENG blocks required fewer opioids pre operatively (mean = 22.67 mg) than did patients who did not receive a PENG block (FIB mean = 26.15 mg and FNB mean = 30.90 mg). Of note, patients receiving PENG blocks required fewer opioids in the 0-6 hours period immediately post block (mean = 3.00 mg) than did patients who did not receive a PENG block (FIB mean = 6.38 mg and FNB mean = 9.10). These results were not statistically significant ($p = 0.5$). The null hypothesis was retained. One adverse event relating to PENG blocks was documented in the records (failed block).

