Provides anaesthesia to the lateral femoral cutaneous nerve, which innervates the site of skin incision for surgical repair (in lateral approaches only)	Anaesthesia of only some of the nerve branches of the femoral nerve that supply the anterior hip capsule. No blockade of AON [15]. Unlikely to provide blockade of the obturator nerve.
Very low risk for direct neural damage due to remote injection points.	Prolonged onset due to distant injection point and slow spread.

PERICAPSULAR NERVE GROUP BLOCK

A preliminary audit at Lismore Base Hospital performed in May 2019, results show a trend toward reduced pain and morphine requirements n=6. The difference was not statistically significant.

ADVANTAGES	DISADVANTAGES
Utilises bony sonographic anatomy, therefore less variations in performance is expected.	Deeper site of infiltration requires higher technical skills.
Target site contains nerves branches that innervate the anterior hip capsule with greater frequency than FNB or FICB. Only technique that blocks the AON [15, 23]. Closer proximity to obturator nerve branches than other techniques [15]. Makes obturator blockade very likely..	Sonographic anatomy not familiar to emergency physicians. Requires re-training and experience in ultrasound guided needle techniques.
Targets small, distal purely sensory nerves [15, 23]. This should convey a faster onset and more complete blockade. Rapid onset is particularly valuable in the emergency department, where the patient is likely to be moved soon after the block is inserted.	Not well established clinical practice. Quality evidence not yet produced.
Infiltration site is distant from major vasculature, so LAST is less likely. It is distant to any motor nerves which eliminates the risk for major motor nerve damage.	

Aims and Objectives

1. To confirm that the PENGGB is a safe and effective intervention for analgesia of patients presenting to the emergency department with hip fractures.
2. To perform a prospective observational study to assess the PENGGB comparing analgesic efficacy vs current practice of FICB and FNB

Null hypothesis

The PENGGB provides comparable analgesia to patients with fractured neck of femur compared to the FNB and FICB.

Study Design

A prospective observational study.

Current Practice:

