All patients presenting to Lismore Base Hospital with fractured neck of femur (#NOF) are placed on the NOF pathway. The pathway suggests that patients on the NOF pathway should receive regional anaesthesia (nerve block) within 30 minutes of arriving at the Emergency Department. The nerve block performed will be determined by the treating clinician.

Inclusion and Exclusion Criteria

Inclusion Criteria

1. Adult patients (>18 years) presenting to Lismore Base Hospital Emergency Department with radiologically confirmed #NOF. The neck of femur fractures include:
 - a. Sub-capital fracture
 - b. Surgical neck fracture
 - c. Intertrochanteric fracture
 - d. Peritrochanteric fracture
2. The patient receives a nerve block for their fractured neck of femur in the Lismore Base Hospital Emergency Department
3. The nerve block may occur before or after the radiological confirmation of diagnosis

Exclusion Criteria:

1. Regional anaesthesia not provided in the Lismore Base Hospital Emergency Department
2. Allergy to amide local anaesthetics
3. Infection of the skin overlying at the overlying the site of potential nerve block
4. The patient has already received a nerve block for this fracture prior to arrival in at Lismore Base Hospital
5. Other reason at the discretion of clinician/s
6. Femoral shaft fracture

Block Standardisation

As this is an observational study, intervention is not dictated by the study, but is at the discretion of the treating physician. However, there have been efforts to standardise aspects of the care provided to improve the validity of this observational data.

In accordance with usual standards of practice:

- All nerve blocks are to be performed with ultrasound guidance. Needle tip and infiltration should be directly visualised with ultrasound.
- All nerve blocks are to be performed with continuous cardiac monitoring and intravenous access.

Nerve Block Kit:

To encourage standardisation of nerve blocks within hour department a nerve block kit is already in use. It contains:

- 80 mm x 21 gauge Pajunk SonoSpot needle (or alternative needle stocked by the department)
- 0.9% sodium chloride - 1 x 10mL vial
- 20 mL luer lock syringe
- 3 mL luer lock syringe
- Drawing up needle
- 25 gauge 38 mm or 23 gauge 35mm needle for local infiltration
- Dressing kit
- Chlorhexidine 2% in 70% ethanol skin prep solution (30 mL)
- Sterile ultrasound probe cover and gel

Standard Order Set:

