A standard order set [Appendix 1] has been built into FirstNet (the electronic medical record). This order set includes blood tests, radiography, referrals and analgesia. This “NOF order set” has been approved by the #NOF pathway working group and is available to all medical officers in the Emergency Department. The investigators will facilitate Medical Officers to add this order set to their ‘favourite’ orders.

Data To Be Collected

Regional Anaesthesia Provided

- Type of nerve block
- Content of nerve block
- Experience of practitioner

Patient Demographics

- # NOF Subtype
- Baseline characteristics: age, gender, comorbidities, social history, opioid use

Pain Scores

1. Visual Analogue Scale (VAS) [Appendix 6]
 - a. 100mm scale. Measured in 1mm increments. Converted to a score from zero to ten.
 - c. Measured at rest and on movement
2. Pain Assessment in Advanced Dementia (PAINAD) [Appendix 6]
 - a. Paper or electronic calculator
 - b. Scored zero to ten

Patients who are cognitively intact will have pain scores measured using the VAS, converted to score from zero to ten.

Patients who have a history of significant dementia or who clinically have significant cognitive impairment will have pain scored by a nurse or doctor using the pain assessment in advanced dementia (PAINAD) score, also zero to ten.

Subjective Observed Patient Comfort During Nursing Cares

- A binary measure of analgesia. Adequate or inadequate?

Opioid intake

- At baseline
- Pre-hospital
- In ED prior to regional analgesia
- After regional analgesia

Standard Documentation

Documentation that is recorded as a usual part of patient care

Nerve Block: Clinicians will be encouraged to document the placement of nerve block and its content in a standardised fashion within the patient's medical record, as is usual practice.

Pain Scores: Pain scores are recorded in the electronic medical record alongside vital signs. This is usual practice of nursing staff in the emergency department and on surgical wards. The utilisation of the VAS pain score is however, a departure from usual practice. Other pain scores such as the numerical pain scale and faces pain scale are previously / currently used by nursing staff at Lismore Base Hospital.

Analgesia Intake: Will be recorded in the electronic medical record. This is usual practice.

Additional Documentation

Documentation that is additional to usual practice, for the purpose of this study

Additional Paper Documentation:

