- ❑ Documentation on a paper form SPIED ED Data Form [Appendix 4] in the emergency department. This is additional to usual documentation and may be replaced by utilising Medical Surveys for data entry in the ED.
- ❑ Subjective Observed Patient Comfort During Nursing Score. May be completed in paper form [Appendix 7] or within Medical Surveys.

Data Governance

Data Storage:

The completed SPIED ED Data Form [Appendix 4] will be filed by clinicians in a folder within the Acute clinical area of the Emergency Department at Lismore Base Hospital. The SPIED ED Data Form will be the enrolment record.. Completed forms will be frequently collected by the investigators and stored securely with the ED Support Offices, which require swipe card access. This data will be stored for 5 years after the completion of data collection and then destroyed.

All other paper forms associated with the SPIED Study will form part of the patient's hospital record and will be treated accordingly.

Data Access:

- Investigators who are clinicians at Lismore Base Hospital have access to the patient's electronic medical records in the usual fashion as they would for day to day clinical work.
 - Investigators who access a patient's file for the purpose of data collection rather than clinical care, will create an electronic entry to document that they are accessing the file for the purposes of the SPIED study.
- In the event that any research funding is obtained, a research assistant may have access to Medical Surveys data and eMR as do the investigators.

Statistical Analysis

Primary Outcome:

Reduction in pain scores over the first 12 hours after nerve block. We will apply the following statistical tests:

- Student's t-test to compare the reduction in pain score of patients who receive a PENGGB compared to FNB and FICB
 - Subgroup analyses of the cognitively impaired and non-cognitively impaired population. These populations will have pain scored by the PAINAD and VAS respectively.
 - Subgroup analysis of FNB and FICB separately

Secondary Outcomes

- Onset of block. Defined as the time until the first pain score ≥ 1.5 less than the pre-block pain score.
 - T-test
- Subjective observed patient comfort during nursing cares
 - Chi Square test
- Patient Preference in the event of crossover
 - Chi Square test
- Rates of block failure. Defined as not achieving a reduction in pain score of $\geq 1.5 / 10$
 - Chi square test

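### Eligibility and grouping by block received leave abandoned or converted block attempts uncounted, so failure rates are conditional on technical success

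*Protocol*

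**What the plan says.** All references are to the protocol.

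- **Eligibility** (Inclusion and Exclusion Criteria). Inclusion 2: "The patient receives a nerve block for their fractured neck of femur in the Lismore Base Hospital Emergency Department". Exclusion 1: "Regional anaesthesia not provided in the Lismore Base Hospital Emergency Department".
- **Choice of block** (Current Practice). "The nerve block performed will be determined by the treating clinician".
- **Grouping** (Statistical Analysis, Primary Outcome). "Student's t-test to compare the reduction in pain score of patients who receive a PENGGB compared to FNB and FICB".
- **Block data** (Data To Be Collected). The list is "Type of nerve block", its content and the practitioner's experience. It has no item for a block that was attempted first, abandoned or converted.
- **Block failure** (Secondary Outcomes and Statistical Analysis). Failure means that the pain score never improves by at least 1.5 out of 10. No procedural failure is defined.
- **Crossover** (Secondary Outcomes). This covers only repeat blocks in the preoperative phase, chosen by the pain service or anaesthetist. It does not cover a change of block within the ED.
- **Technical difficulty** (Comparison of Nerve Blocks). PENG disadvantages include "Deeper site of infiltration requires higher technical skills", together with unfamiliar ultrasound anatomy and a need for retraining. The same section expects PENG performance to vary less because it uses bony landmarks. For the femoral nerve block (FNB) it lists poorly contrasted nerve tissue, and distorted anatomy in some patients with vascular disease.

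**The concern.** Three kinds of patient fall outside these rules, or are placed by default:

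1. **A block is attempted and abandoned, and none is given.** The patient fails inclusion 2, meets exclusion 1 and never enters the study.
2. **A block is attempted and converted to another type in the ED.** The patient qualifies through the second block and is most naturally counted under it. If that block works, the patient is a success for it and the first attempt leaves no trace.
3. **Two blocks are given in the ED.** The patient is eligible, but no rule says which group applies.

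No other outcome recovers these attempts. The failure endpoint uses pain scores, and the adverse-event keywords (delirium, sedation, constipation, aspiration, naloxone) would not find an abandoned needle pass.

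The first aim is to confirm that PENG is safe and effective in ED patients, and Outcomes and Significance expects a good result to increase uptake in other EDs. An ED weighing adoption needs to know what happens when a clinician sets out to do the block, including how often it cannot be completed. The sample size also rests on a one-sided non-inferiority test, so if the unrecorded losses were mostly PENG attempts, a false finding of non-inferiority would become more likely.

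**Working it through.** **1. The plan's own figures.** Inputs from Sample size and statistical power: one-sided 0.05, SD 2.4, difference 1.5, ratio 1:2, power 0.80. The normal approximation for the smaller group is (1 + 1/2) × (2.4 × (1.645 + 0.842) / 1.5)² = 23.7, so 24 + 48 = 72. On the t distribution, power is 0.797 at 24 + 48 and 0.809 at 25 + 49, consistent with the stated 74 (25 + 49). The early-termination target also reproduces: 41 + 84 gives two-sided power 0.805 for a difference of 1.3. Neither figure is in dispute, and the fix changes neither.

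**2. Assumptions.** The protocol gives no abandonment or conversion rate. Let c be the share of PENG attempts abandoned or converted, assumed to be 5–17%. The upper end is numerically the audit's one failed block among six PENG blocks (exact 95% interval for 1/6: 0.4% to 64%). It is a placeholder, since that block may not have been an abandoned attempt. Also assume that 10% of completed PENG blocks fail on pain score and that completed blocks average a reduction of 4, one of the two planning means.

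**3. Patients affected** (attempts × c).
- 25 attempts: 25 × 0.05 = 1.25 to 25 × 0.17 = 4.25, or about 1 to 4.
- 41 attempts: 41 × 0.05 = 2.05 to 41 × 0.17 = 6.97, or about 2 to 7.

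**4. Failure rate by attempt**, each abandoned or converted attempt counted as a failure: c + (1 − c) × 0.10.
- c = 0.05: 0.05 + 0.95 × 0.10 = 14.5%.
- c = 0.17: 0.17 + 0.83 × 0.10 = 25.3%.
- By block received: 10% in both cases.

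**5. Overstatement of the PENG mean**, if affected patients have mean reduction r: c × (4 − r).

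| r in affected patients | c = 0.05 | c = 0.17 |
|---|---|---|
| 4 (rescue block works as well) | 0 | 0 |
| 2.5 (the other planning mean) | 0.08 | 0.26 |
| 0 (no relief at all) | 0.20 | 0.68 |

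Against the planning difference of 1.5, the last row is 0.20/1.5 = 13% to 0.68/1.5 = 45%. If patients with no relief were also counted among 49 comparator patients averaging 4, the comparator mean would fall by 0.10 (c = 0.05) or by 4 − (49 × 4)/(49 + 4.25) = 0.32 (c = 0.17). That case needs a completed rescue block that gives no relief in any converted patient, so it is an extreme.

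**The case against.** **Grouping by block received is legitimate.** In an observational study whose second aim is comparative analgesic efficacy, the effect of the block delivered is a fair question, and the effect by attempt is a different one. Making first-attempt grouping primary would also credit PENG with relief from a rescue FNB or fascia iliaca compartment block (FICB). That pulls the difference towards zero and can itself favour non-inferiority. This stands, and the primary comparison should not be changed on this ground.

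**The rules may exist elsewhere.** The ED Data Form is not shown and may record attempts, and a statistical analysis plan could assign mixed or converted patients. This stands in part: neither could restore patients whom the eligibility criteria keep out.

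**A stronger reading is tempting:** that the plan conceals technical failures it expects of PENG, so that efficacy, failure rate and safety are all biased in its favour. The documents do not support this. They name technical demands but state no expectation of abandoned attempts. They expect less variation with PENG and list obstacles to FNB, so conversion from FNB is possible too. The audit's failed block was recorded against PENG, which shows that a failed block can remain visible under PENG. Likewise, a completed PENG block that does not relieve pain stays in the PENG group and counts as a failure. Nor is a shift of 0.2–0.7 points the expected size: it assumes no relief at all, although converted patients receive another block.

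**Conclusion.** The point holds in a limited form. As written, the protocol loses abandoned attempts, most naturally reassigns converted ones, and has no group for patients given two ED blocks. This applies to PENG, FNB and FICB alike.

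The firmest consequence is that each block's failure rate, and the evidence for the first aim, describe only attempts that were technically completed. On the assumed rates, PENG failure would be reported as 10% where the rate by attempt is about 15–25%. That gap depends on the assumed 5–17% and on counting each abandoned or converted attempt as a failure.

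The effect on mean pain reduction is less certain. It ranges from none, if the rescue block works as well, to about 0.2–0.7 points if affected patients get no relief. The described depth, skill demand and unfamiliar anatomy make a larger loss for PENG plausible, but its direction remains an inference and its size is unknown.

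**What to change.** - **Eligibility.** Reword inclusion 2 so that a patient qualifies once a nerve block is attempted (needle inserted) in the ED, and change exclusion 1 to match.
- **Recording.** Have the ED Data Form capture the first block attempted, whether it was completed, and any further ED block, unless it already does.
- **Failure.** Count an abandoned or converted attempt as a procedural failure of the first block type, for all three blocks, and report this rate alongside the pain-score failure rate.
- **Grouping.** State the group for patients given two ED blocks.
- **Analysis.** Keep the as-received comparison as primary. Add a comparison by first block attempted as a sensitivity analysis, with pain scores timed from the first attempt.

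The cost is protocol wording, one form line and one further analysis. The sample size of 74 is unchanged and no clinical care is dictated. The reported failure rate may look less favourable. The by-attempt comparison will include relief from rescue blocks, so it must be read with care for non-inferiority.

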1. SPIED Study Emergency Department Data Form [Appendix 4]
 - a. Emergency Department staff may choose to use this form in place of Medical Surveys should they prefer, or if there are logistical challenges encountered with Medical Surveys
2. Limb Observation Chart: [Appendix 6]
 - a. It is standard practice on the surgical ward for nursing staff to complete limb observations every 1-2 hours on patients with #NOF and record these on a limb observation chart.
 - b. This chart has been modified for the SPIED study to also record pain scores
 - c. Also includes pain score calculators for the VAS and PAINAD
3. Subjective Observed Patient Comfort During Nursing Cares [Appendix 7]

Primary outcome = reduction of pain score

VAS pain scores will be recorded at rest and on movement. Movement is defined as attempted hip flexion to 15 degrees. PAINAD scores will be single measure based on nursing observation.

This score will be documented at the following times:

- Prior to placement of nerve block in the emergency department
- 15, 30, 60 minutes post placement of block
- With routine limb observations on the surgical inpatient ward, approximately hourly

Data will be collected for 12 hours post nerve block (or the next documented score after 12 hours) or until the patient is moved to the operating room, whichever is sooner.

Sample size and statistical power

The rationale for sample size calculations:

- A reduction in visual analogue pain score of 13 mm (1.3/10) was established as being clinically significant by Todd et al in 1996 [26].
- A clinically significant difference between two treatments that reduce pain scores by 1.3/10 has not been well defined
- Cooper et al used 1.5/10 difference in pain scores as a definition of clinically significant difference between blocks [27].
- Newman et al found a standard deviation in pain score reduction of 2.4 in patients receiving regional analgesia for #NOF in 2013 [28]. This figure was used by Cooper et al for their power calculation in 2018.
- Cooper et al found standard deviations of 2.2 and 2.4 respectively for the FNB and FICB [27].
- A retrospective study of patients that received regional anaesthesia for # NOF at LBH in the first 4 months of 2019 was performed by co-investigators of this study. This data included 40 patients that received regional anaesthesia in ED, 6 of whom received a PENG block. Pain score documentation was not sufficiently reliable to inform power calculations for this observational study.

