This project aims to improve understanding of the PENG block and its effects. We aim to publish results, either positive or negative, in a peer-reviewed journal approved by the Australasiaon College of Emergency Medicine and/or at appropriate scientific meetings.

Justice

All patients presenting to our facility with #NOF will be eligible for inclusion in this study. The patient experience of receiving the PENG block is very similar to that of receiving FNB or FICB and a lay-person would unlikely be able to tell the difference. There is no increased burden on patients enrolled nor on those not enrolled.

Beneficence

We believe that all patients present and future will benefit from the standardisation of practice and the establishment of preferred practice within our health service.

Risk

We do not anticipate that this study exposes participants to an increased risk. As outlined above we believe the PENG block conveys safety advantages compared to standard blocks the FNB and FICB. Most important is the physical separation of the site and the tissue plane of infiltration from major blood vessels. This reduces the risk of local anaesthetic systemic toxicity - which is the most serious adverse event associated with regional anaesthesia. Additionally, the nerves targeted and affected by the PENGGB are small, sensory nerves. Any trauma or toxicity to nerves as a result of a PENGGB would have no effect on motor nerves, which provide power to the thigh. Conversely, both the FICB and FNB effect larger motor nerves and any nerve trauma or toxicity can theoretically affect the muscle power in the thigh. We note that there is poor evidence supporting the argument that regional anaesthesia causes clinically significant trauma or toxicity to motor nerves.

Outcomes and Significance

The PENG block is a new therapy with a sound scientific basis and promising preliminary results both in the limited existing literature and our experience delivering this therapy at Lismore Base Hospital. If it is a superior regional analgesic then it follows that the therapy should be superiorly opioid-sparing. As we know, the study population is particularly at risk of complications from opioid analgesia [5-7]. Also, we know that pain (a result of ineffective analgesia) itself is a risk factor for agitation and delirium [reference] [29-33]. It follows that there would be an improvement in patient safety and patient-important outcomes from wider adoption of a superior intervention.

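### Exclusion 5 is open-ended, has no time limit and needs no recorded reason, so in this non-randomised comparison patients may be excluded after block type and early pain scores are known

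*Protocol*

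**What the plan says.** The list under Inclusion and Exclusion Criteria ends the patient-specific exclusions with "Other reason at the discretion of clinician/s". It does not say which clinician, by when, or whether the reason is written down.

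Three other statements set the order of events:

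- Study Design, Current Practice: "The nerve block performed will be determined by the treating clinician".
- Inclusion 2: "The patient receives a nerve block for their fractured neck of femur in the Lismore Base Hospital Emergency Department".
- Inclusion 3: "The nerve block may occur before or after the radiological confirmation of diagnosis".

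The primary outcome section schedules pain scores before the block, at 15, 30 and 60 minutes after it, and then about hourly on the ward.

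On enrolment, Data Governance states "The SPIED ED Data Form will be the enrolment record" and that the completed form "will be filed by clinicians in a folder within the Acute clinical area of the Emergency Department". Additional Paper Documentation adds "Emergency Department staff may choose to use this form in place of Medical Surveys should they prefer", so the form is one of two routes of entry.

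The text shown contains no consecutive-enrolment rule, no log of patients not enrolled, and no bar on exclusion after the block.

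**The concern.** A discretionary exclusion is common in randomised trials and does little harm there, because it normally acts before allocation. Here there is no allocation step. Exposure is chosen at the bedside, a patient cannot be fully eligible until the block is in, and the first outcome score is due 15 minutes later. An exclusion without a time limit can therefore act after both exposure and early outcome are visible.

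If the chance of being left out depends on block type and response together, the enrolled groups no longer represent the patients who received each block. Baseline adjustment cannot correct this, since the missing patients are not in the data. The effect could run either way, creating an apparent PENG advantage or hiding one. The block-failure rate, a secondary outcome, is directly exposed because poor responders are the patients it counts. With a planned minimum of about 25 PENG patients, a few selective omissions would matter.

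**Working it through.** **1. Can the rule act late?** The stated order is: clinician chooses block; block given (inclusion 2 met); radiology, which may come after the block (inclusion 3); scores at 15, 30 and 60 minutes. Eligibility is complete only at or after the block. Exclusion 5 is tied to no step in that sequence, so the text permits its use after the early scores.

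**2. The plan's own figures.** Inputs from Sample size and statistical power: one-sided 0.05, power 0.80, SD 2.4, difference 1.5, ratio 1:2.

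- Normal approximation, smaller group: (1 + 1/2) × [2.4 × (1.645 + 0.842)/1.5]² = 23.7, so 24 + 48 = 72.
- Exact t-test power is 0.797 at 24 + 48 and 0.809 at 25 + 49. The stated 74 (25 + 49) is reproduced.
- Accrual: (203 + 79)/18 = 15.67 a month; 15.67 × 6 = 94 presentations; × 0.8 = 75.2 enrolled; one third = 25.1 PENG.

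The 80% multiplies all presentations. The roughly 19 patients not enrolled (94 − 75.2 = 18.8) therefore include some never blocked in the ED, and are not a loss within one block group.

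**3. Illustrative shift.** Assume normal reductions with SD 2.4 and that the lowest fraction f of one group is left out. The mean of that group rises by SD × φ(z_f)/(1 − f).

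| f | Shift | Share of 1.5 |
|---|---|---|
| 5% | 2.4 × 0.1031/0.95 = 0.26 | 17% |
| 10% | 2.4 × 0.1755/0.90 = 0.47 | 31% |

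**4. Effect on the test.** Simulation with 40,000 runs, 25 v 49, pooled t-test, 1.5 taken as the non-inferiority margin, worst responders left out of the PENG group only until 25 are enrolled:

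| Left out | False non-inferiority (PENG truly worse by 1.5) | False PENG superiority (blocks equal, two-sided 0.05) |
|---|---|---|
| none | 5% | 2.5% |
| 1 of 26 | 10% | 5% |
| 3 of 28 | 21% | 13% |

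**5. What shrinks it.**

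- *Same share lost in both groups.* At about 10% in each, the simulated bias in the difference was 0.05 points. Most of that reflects rounding to whole patients (3 of 28 against 5 of 54).
- *Selection on an early score, not on the 12-hour outcome.* The shift is multiplied by the correlation between the two. At 0.5, an assumed value, 0.26 becomes 0.13 and 0.47 becomes 0.23.

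**The case against.** The best counter-case has five parts.

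- **Failed blocks are meant to stay in.** Block failure is a defined and tested secondary outcome, and nothing authorises exclusion for a poor result. That is a fair reading of intent, but the criterion as worded does not secure it.
- **Study scoring starts before the block, and investigators collect forms frequently.** This helps, but neither provision fixes enrolment at that point. All hip-fracture patients are on the pathway and the investigators have record access, so omissions could be traced. The Protocol does not commit to tracing them.
- **Appendices may settle the timing.** The enrolment checklist, the inclusion-exclusion appendix and the consent appendix are listed but not shown. If one of them fixes when exclusion 5 applies, the main text need only say the same.
- **The illustration is generous to the concern.** It assumes exact truncation on the outcome in one group only. ED staff see at most the early scores, while the outcome runs over 12 hours and is scored largely on the ward. This stands, and the figures should be read as illustrations.
- **The two wording points are minor.** The Justice section says "All patients presenting to our facility with #NOF will be eligible for inclusion in this study". Read literally this conflicts with every exclusion, but it is a statement about fair access. The interchange of the ED form with Medical Surveys is loose wording about data entry and is not in itself a route to selection.

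A reader might also infer that the person who performed the block decides the exclusion. The criterion says only clinician/s, undefined. Nothing prevents it being the operator, and nothing shows that it is.

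**Conclusion.** The point holds as a defect in the rule. It is not evidence that selective exclusion has occurred or will occur. The Protocol permits an unexplained exclusion after block type and early pain scores are known, and no text shown forbids it. Bias follows only if such exclusions differ by block, and its size cannot be derived from the document. Under the stated assumptions, losing the worst 5% or 10% of one group moves its mean by 0.26 or 0.47 points. The shift is smaller if selection acts on early scores, and the bias in the comparison is near zero if both groups lose the same share.

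A stronger reading would treat the planned 20% non-enrolment as the worst fifth of one group, which by the same formula gives 0.84 points or 56% of the 1.5-point difference. The arithmetic is right but the input does not transfer: the 20% applies to all presentations, including patients with no ED block, and the document supports no such loss within a group.

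Eligibility and the definition of enrolment are protocol matters, and an analysis plan could not recover the missing patients.

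**What to change.** - Delete exclusion 5, or limit it to a reason recorded before needle insertion.
- State that no patient is excluded after the block except for failing a listed criterion, for example a fracture not confirmed on imaging.
- Have the investigators keep a log, drawn from the electronic record, of all hip-fracture patients blocked in the ED. Report those not enrolled by count, block type and reason.
- Let either the ED Data Form or the Medical Surveys entry count as the enrolment record.
- Bring the Justice sentence into line with the listed criteria.

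The log should be a screening record and not a replacement for the analysed cohort. Clinicians are only encouraged to document the block in a standard way, the VAS departs from usual practice, and the local audit found pain scores too unreliable for a power calculation. Patients found only through the record would often lack the primary outcome and be reportable only as counts. The log may also miss blocks that were poorly documented.

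The cost is a few lines of protocol text and some investigator time to reconcile the list. The sample size of 74 is unchanged.
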